10.0 STATISTICAL METHODS

10.1 Statistical Plan

A Statistical Analysis Plan (SAP), including study data report format, detailing the intended statistical analysis of the study data, will be prepared as a separate document and finalized before database lock. Any deviation from the original statistical plan will be described and justified in the final report, as appropriate. The procedure for accounting for missing, unused, and spurious data will be included in the SAP.

If not otherwise specified, statistical significance is defined as $p < 0.05$, two-sided. Data will be summarized with respect to demographic and baseline characteristics, efficacy variables, and safety variables. For categorical variables, the number and percent of each category within a parameter will be calculated for non-missing data. For continuous variables, statistics will include number of observations, mean, standard deviation, median, minimum, and maximum values.

All statistical analysis will be conducted using Statistical Analysis Software (SAS[®]), Version 9.4 or higher. Datasets will be prepared using headings from Clinical Data Interchange Consortium (CDISC), Study Data Tabulation Model (SDTM) implementation for human clinical trials, and Analysis Dataset Model (ADaM).

10.2 Sample Size Determination

The sample size of approximately 50 patients was deemed appropriate to meet the objectives of the study.

CONFIDENTIAL PROTOCOL

An Evaluation of the Reduction in Erythema by RHOFADET™ (oxymetazoline hydrochloride) Topical Cream, 1% (Allergan) in Adult Patients with Moderate to Severe Persistent Facial Erythema Associated with Rosacea.

10.3 Protocol Deviations/Violations

This study will be conducted as described in this protocol except for an emergency situation in which the protection, safety, and well-being of the patient requires immediate intervention, based on the judgment of the Investigator or a responsible, appropriately trained and credentialed professional(s) designated by the Investigator. In the event of a significant deviation from the protocol due to an emergency, accident or mistake, the Investigator or designee must contact Perrigo [REDACTED] at the earliest possible time.

[REDACTED]

[REDACTED]

[REDACTED]

10.4 Study Populations

10.4.1 Per-Protocol (PP) Population

The PP population will include all randomized patients who:

- Meet all inclusion and exclusion criteria.
- Complete the final study visit within the protocol window of Day 15 ± 2 days (Day 13 to Day 17 inclusive).
- Have no significant protocol deviations (PDs) that would affect treatment evaluation.
- Apply the study product appropriately [REDACTED]
[REDACTED].
- Do not miss the scheduled applications for more than one consecutive day.

[REDACTED]

[REDACTED]

CONFIDENTIAL PROTOCOL

An Evaluation of the Reduction in Erythema by RHOFADETM (oxymetazoline hydrochloride) Topical Cream, 1% (Allergan) in Adult Patients with Moderate to Severe Persistent Facial Erythema Associated with Rosacea.

10.4.2 Modified Intent-to-Treat (mITT) Population

The mITT population will include: randomized patients who:

- Meet all inclusion/exclusion criteria.
- Administer at least one dose of assigned product.
- Have at least one post-baseline evaluation.

Patients discontinued early for reasons other than lack of treatment effect or worsening condition will be included in the mITT population using last observation carried forward (LOCF).

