9.3.4 Removal of Patients from the Study

Patients will be advised that they are free to withdraw from the study at any time. If necessary, the Investigator may withdraw a patient from the study to protect the health of that patient. If a patient terminates from the study early, all efforts will be made to complete Visit 4 study procedures. For early termination, the Investigator will fully document the reason for early termination. The clinical report will include all reasons for early withdrawals.

Reasons for removal may include the following:

- Patient withdrew consent.
- Significant adverse event (AE) that led the Investigator or patient to withdraw for safety reasons.
- Non-compliance with protocol requirements (e.g., use of restricted medication, not following dosing procedures, failure to make scheduled study visits in a timely fashion).
- Pregnancy
- Significant worsening of rosacea such that the Investigator and/or patient believes it is in the best interest of the patient to withdraw from the study and be provided alternative treatment.
- Participant enrolls in another clinical trial, or is found to have previously enrolled in this clinical trial.

Patients who withdraw or are removed from the study will not be replaced. All patients who are randomized will be included in the safety monitoring tabulating all AEs experienced after dosing.

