11.2.4 Source Documents and Case Report Forms

All patients will be identified by initials, date of birth, and a unique patient number. Source documents will be used to record all study-related data. Source document entries will be used to complete eCRFs. A set of eCRFs will be completed for each patient randomized in the study. All data and eCRFs will be reviewed, evaluated, and signed by the Investigator.

The original source documents and a copy of the corresponding eCRFs will be retained by the Investigator. Patients who terminate early from the study will have the Visit 4 (End of Study) source/eCRF completed.

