#### Modified Intent-to-Treat (mITT) Population

The mITT population will include: randomized patients who:

- Meet all inclusion/exclusion criteria.
- Administer at least one dose of assigned product.
- Have at least one post-baseline evaluation.

Patients discontinued early for reasons other than lack of treatment effect or worsening condition will be included in the mITT population using last observation carried forward (LOCF).

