**8.5 Methods for Handling Missing Data**

For demographic and baseline characteristics, each variable will be analyzed using all available data. Patients with missing data will be excluded only from analyses for which data are not available.

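### Does the mITT wording leave patients who stop for lack of effect or worsening out of the efficacy analysis?

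*Protocol*

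**What the plan says.** The mITT text is the same in Protocol 10.4.2 and SAP section 7. Three criteria define membership: eligibility, at least one dose, and the third, "Have at least one post-baseline evaluation". None of them refers to the reason for stopping. A further sentence in the Protocol says that those who stop early for "reasons other than lack of treatment effect or worsening condition will be included in the mITT population using last observation carried forward (LOCF"). The SAP has the same sentence, worded "Patients discontinued early for reasons other than lack of treatment effect or worsening condition will be included in the mITT population", and likewise attaches LOCF to that group. Neither section says what value is used for patients who stop for lack of effect or worsening.

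Protocol 10.1 passes the general question on: "The procedure for accounting for missing, unused, and spurious data will be included in the SAP". SAP 8.5, the section on missing data, begins "For demographic and baseline characteristics, each variable will be analyzed using all available data". It adds that a patient with missing data is left out only of the analyses that need those data. It does not mention efficacy data.

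Protocol 9.3.4 lists as a reason for removal "Significant worsening of rosacea such that the Investigator and/or patient believes it is in the best interest of the patient to withdraw". The same section says "If a patient terminates from the study early, all efforts will be made to complete Visit 4 study procedures", and Protocol 11.2.4 adds "Patients who terminate early from the study will have the Visit 4 (End of Study) source/eCRF completed".

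**The concern.** The LOCF sentence sorts early stoppers by a reason that is itself an outcome. Those who stop for unrelated reasons get a carried-forward value. For those who stop because the product did not work, nothing is stated. A reader could infer that they are outside the mITT population, or inside it with no end-of-study value. Worsening is a listed removal reason, so the case is foreseen, and the SAP section that a reader would turn to speaks only of demographic and baseline variables.

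If failures were left out, selection would depend on response. The mean reduction in erythema would be too favourable, and a single-arm study has no control group in which the bias could cancel. SAP section 2 also lists estimation of between-patient variability (the variable itself is redacted). Removing the worst responders would usually make that SD too small.

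**Working it through.** **Step 1: what the text implies for a failure.** Take a patient who is eligible, has been dosed, has one post-baseline evaluation, and then stops for worsening.

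| Reading | Support in the text | Consequence |
|---|---|---|
| Outside the mITT population | None direct. It must be inferred from the LOCF sentence and contradicts the three criteria, which this patient meets. | Biased |
| In, but with no end-of-study value | Possible only if nothing was assessed at termination, or if the assessment is ignored. | Biased in an end-of-study analysis |
| In, with the early-termination Visit 4 data | The three criteria, plus Protocol 9.3.4 and 11.2.4. The heading of Protocol 9.5.4 also makes Visit 4 the early-termination visit. | No bias from selection |

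The LOCF sentence contains neither the word *only* nor any exclusion. It says how one group is completed. The third reading is the only one that uses every relevant provision without conflict. The second sentence of SAP 8.5, if read more widely than baseline variables, fits it too: a patient with a Visit 4 value has data for that analysis and stays in.

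**Step 2: where another rule could be.** There are redacted blocks after the per-protocol criteria in both documents; in the SAP they come directly before the mITT text. SAP section 6 and SAP 8.2 are redacted, and Protocol 10.6 to 10.8 show no content. A rule for treatment failures would naturally sit in one of these. Text that is blacked out is not absent from the plan.

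**Step 3: size if failures were nevertheless left out.** The documents give n of about 50 and no failure rate, effect size or SD, so there is no plan figure to reproduce. Assume k failures among 50, with a mean d SD worse than the others, where SD is that of the others, d = 1 to 3 and p = k/50.

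- Overstatement of the mean = p × d.
- SD without failures ÷ SD with them, if failures are as spread out as the others = 1/√(1 + p(1 − p)d²).

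| k | p | Mean overstated by (SD), d = 1 to 3 | SD ratio, d = 1 to 3 |
|---|---|---|---|
| 1 | 0.02 | 0.02 to 0.06 | 0.990 to 0.922 |
| 2 | 0.04 | 0.04 to 0.12 | 0.981 to 0.862 |
| 5 | 0.10 | 0.10 to 0.30 | 0.958 to 0.743 |

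Example, k = 2 and d = 3: the shift is 0.04 × 3 = 0.12, and the ratio is 1/√(1 + 0.0384 × 9) = 1/√1.3456 = 0.862.

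For scale, the 95% confidence half-width of a mean at n = 50 is t(0.975, 49)/√50 = 0.284 SD. With five failures the shift exceeds this only if d is above 0.284/0.10 = 2.84. The 95% interval for an SD at n = 50 runs from 0.835 to 1.246 times the estimate. The ratios for one or two failures are no further from 1 than that lower limit.

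The SD need not shrink. If the failures cluster tightly, with no spread of their own, the ratio is 1/√((1 − p) + p(1 − p)d²). At d = 0.5 this gives 1.008, 1.016 and 1.041 for 1, 2 and 5 failures. In simulation with equal spread, k = 1 and d = 1, leaving the failure out lowered the sample SD in only 52% of samples.

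**The case for a change.** The strongest argument for a change is that a definition of an analysis set should not need inference. If the three criteria already settle membership, the qualifier about reasons must restrict something, and the sentence does not say whether it restricts inclusion or only LOCF. The mITT paragraphs themselves carry no redaction mark and point to no other rule, and SAP 8.5, also without a redaction mark in its text, does not fill the gap. The visible per-protocol criteria require the final visit on Day 13 to 17, so a patient who fails earlier would not meet them, and the mITT is the efficacy set in which that patient's status has to be settled. The study is open-label, so a rule chosen late could be chosen by someone who knows who failed. One sentence in each document would close the matter.

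Part of this stands. The readable text gives no value for these patients, and a cross-reference would have helped. But missing detail in the readable text does not show a wrong rule, and nobody can say that unseen text conflicts with the mITT paragraphs. Writing in a new rule without sight of the redacted sections could duplicate or contradict one that already exists. Nor would the obvious sentence remove all optimism. Where no early-termination assessment was made, carrying forward the last value may use a reading taken before the worsening. A protocol revision also needs IRB review under Protocol 11.2.3, so it is not free.

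**Conclusion.** No change follows. In the readable text this is a gap that an analyst would fill sensibly: a patient who meets the three criteria is in the mITT population whatever the reason for stopping, and the early-termination Visit 4 assessment supplies the value. That reading brings no selection bias, and it is the one that the criteria and the data-collection provisions support together.

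Harm would need four things at once: failures occur, no redacted rule covers them, they are left out against the criteria as worded, and the affected endpoint is analysed in the mITT population (the readable text does not show which population is used). If all four held, one or two failures in 50 would move the mean by at most 0.12 SD under the assumed range of 1 to 3 SD, well within the 0.28 SD half-width. Only about five failures at close to 3 SD would reach the size of that sampling error. These figures rest on assumed failure counts and distances. The documents do not allow the true size to be derived, and with no failures it is zero. Anyone holding the unredacted documents can settle the remaining doubt by reading the efficacy sections.

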10.4.3 Safety Populations

The Safety population will include all patients who are randomized and received study product.

10.5 Baseline Comparability

Baseline characteristics will be evaluated separately for the PP, mITT, and Safety populations.

The following baseline demographics (determined from their initial study visit) will be evaluated:

- Age (years)
- Sex (Male/Female)
- Ethnicity (Hispanic/non-Hispanic)
- Race (White, Black/African American, Native Hawaiian or Other Pacific Islander, Asian, American Indian, or Alaska Native)
- Baseline number of inflammatory lesions (i.e., papules and pustules)
- [REDACTED]
- [REDACTED]
- [REDACTED]

Summary tables by treatment group will be presented. Continuous variables will be summarized using descriptive statistics (number of observations, median, minimum, maximum, mean, and SD). Categorical variables will be summarized using frequencies and percentage. Baseline treatment comparisons will be presented using Chi-Square or Cochran-Mantel-Haenszel tests for the categorical variables, and Analysis of Variance (ANOVA) for the continuous variables.

All data will be listed by treatment and patient.

10.6 Efficacy Variables

10.7 Efficacy Endpoints

Primary Efficacy Endpoints

CONFIDENTIAL PROTOCOL

An Evaluation of the Reduction in Erythema by RHOFADE™ (oxymetazoline hydrochloride) Topical Cream, 1% (Allergan) in Adult Patients with Moderate to Severe Persistent Facial Erythema Associated with Rosacea.

10.8 Efficacy Analysis

CONFIDENTIAL PROTOCOL

An Evaluation of the Reduction in Erythema by RHOFADETTM (oxymetazoline hydrochloride) Topical Cream, 1% (Allergan) in Adult Patients with Moderate to Severe Persistent Facial Erythema Associated with Rosacea.

10.9 Safety Analysis

Adverse events will be classified using standard Medical Dictionary for Regulatory Activities (MedDRA) terminology Version 20.0 or higher. Summary tables including the type, date of onset, date of resolution, incidence, severity, relationship to the study product, action taken, and outcome will be prepared for AEs.

Concomitant medication use, including medication name, start date, stop date, and reason for use during the randomized treatment period will be tabulated by patient.

11.0 REGULATORY OBLIGATIONS

11.1 Institutional Review Board

The study protocol, ICF, Investigator's Brochure, or package insert (as applicable), and any specific advertising will be submitted to, and approved by, an IRB before the start of the study. A form must be signed by the chairman or designee of the IRB noting the approvals. This notification of the board's approval along with a description by profession and gender of the board's composition will be provided to the Sponsor.

11.2 Study Documentation

This study will be conducted in compliance with the protocol; Good Clinical Practices (GCPs) and all applicable regulations, including the Federal Food, Drug, and Cosmetics Act, US applicable Code of Federal Regulations (title 21), parts 50, 56, 312, 320, and any IRB requirements relative to clinical studies; and the Declaration of Helsinki, June 1964, as modified by the 64th World Medical Association General Assembly, October 2013.¹⁷⁻²⁰ The Investigator will permit trial-related monitoring, audits, IRB review and regulatory inspections providing direct access to source data/documents.

11.2.1 Protocol

The Investigator indicated on FDA Form 1572 will act as the Principal Investigator at each study site. Protocols will be noted as approved by placement of the [REDACTED] Representative's signature on the cover page. The Sponsor of the study will also approve the protocol by having a study-responsible individual sign the protocol cover page.

CONFIDENTIAL PROTOCOL

An Evaluation of the Reduction in Erythema by RHOFADETTM (oxymetazoline hydrochloride) Topical Cream, 1% (Allergan) in Adult Patients with Moderate to Severe Persistent Facial Erythema Associated with Rosacea.

11.2.2 Informed Consent

An ICF that includes all of the relevant elements currently required by FDA and local state regulations will be provided to each prospective study patient before being screened into the study. The type and method of study, tests to be administered, any potential or possible hazards, and the patient's right to withdraw from the study at any time will be explained to the patients by the Investigator or designee. Once the Investigator or designee is assured that an individual candidate understands the implications of participating in this study, the patient will be asked to give consent by signing and dating in the appropriate areas of the ICF. The Investigator or designee will also sign and date the form, along with a staff member who will sign the ICF as a witness to verify that the patient has indeed received information. If any other language is required, translation will be performed by a certified translator. A copy of the ICF will be provided to the patient.

11.2.3 Protocol and Informed Consent Changes

Sponsor approved changes to the protocol or the ICF will be implemented as revisions to the original documents and will require additional review and approval by the IRB. Revisions to the original protocol will be documented in amendments, incorporated as a preface to the new version. Any revision that substantially alters the study design or increases potential risk to the patient requires the patient's consent to continue in the study. The approvals will be processed in accordance with the established IRB procedures. Copies of all protocol and ICF amendments/revisions, along with letters noting IRB approval, will be submitted to the Sponsor.

11.2.4 Source Documents and Case Report Forms

All patients will be identified by initials, date of birth, and a unique patient number. Source documents will be used to record all study-related data. Source document entries will be used to complete eCRFs. A set of eCRFs will be completed for each patient randomized in the study. All data and eCRFs will be reviewed, evaluated, and signed by the Investigator.

The original source documents and a copy of the corresponding eCRFs will be retained by the Investigator. Patients who terminate early from the study will have the Visit 4 (End of Study) source/eCRF completed.

11.2.5 Drug Accountability

All study product receipt, inventory, dispensing, dosing, and reconciliation records will be maintained in compliance with federal regulations. The study product will be dispensed to qualified study patients according to established procedures. At the end of the study (after the database has been locked) all used and unused study product will be returned to Sponsor or designee.

11.2.6 Drug Storage

Study product will be stored at controlled room temperature of 20-25°C (68-77°F) with excursions permitted to 15-30°C (59-86°F) in a secure place with access by authorized individuals only. The Investigator will be responsible for maintaining accurate records of drug

CONFIDENTIAL PROTOCOL

An Evaluation of the Reduction in Erythema by RHOFADETTM (oxymetazoline hydrochloride) Topical Cream, 1% (Allergan) in Adult Patients with Moderate to Severe Persistent Facial Erythema Associated with Rosacea.

receipt, dispensing, and return. After finalizing the study report, all partially used and unused study product will be returned to Sponsor or designee.

11.2.7 Retention of Reserve Samples

No reserve samples are required for this study.

11.2.8 Return of Clinical Supplies

All unused kits of study product will be returned to [REDACTED].

11.2.9 Reporting Safety Information to the IRB

The Investigator must promptly report to the Investigator's IRB all unanticipated problems involving risks to patients. This includes death from any cause and all SAEs occurring during the study, regardless of the assessed causality.²¹

11.2.10 Record Retention

All study product accountability records, eCRFs, source data, and related regulatory documents must be retained according to 21 CFR 312.62(c) for a period of 2 years following the date the marketing application is approved for the study product for the indication for which it is being investigated; or, if no application is to be filed or if the application is not approved for such indication, until 2 years after the investigation is discontinued and FDA is notified. The Sponsor will be notified before any destruction of records.

11.2.11 Study Monitoring and Auditing

[REDACTED] will be responsible for monitoring the study according to GCP and applicable regulations. Monitoring visits are for the purpose of confirming adherence to the protocol and to verify complete and accurate data collection. The clinical site will make all records associated with the study available to [REDACTED] representative during such visits and audits.

The study may be subject to audit by the Sponsor, Sponsor Representative, or by regulatory authorities. If such an audit occurs the Investigator must agree to allow access to required patient records. By signing this protocol, the Investigator grants permission to personnel from the Sponsor, its representatives, and appropriate regulatory authorities for on-site monitoring of all appropriate study documentation, as well as on-site review of study procedures.

11.2.12 End of the Trial

The end of the trial is defined as the time at which the last patient has completed their last visit in the study. Upon completion of the study, the study product will no longer be available to the patient but the Investigator can, at their discretion, discuss alternative treatments with the patient.

